## **V. FUNDING**

---

This study is expected to be funded by a grant from NIDA.

## **VI. ABOUT THE SUBJECTS**

---

Ethnic diversity of this sample is expected to be representative of the greater Boulder-Denver area at large. A trained research assistant will screen prospective participants who call, email, or complete an online survey, according to the inclusion/exclusion criteria listed below. Given established associations with inflammatory markers (e.g. IL6, TNFa), we will exclude individuals who report an immune-related disease (e.g. HIV), use of maximal doses of steroids, or use of psychotropic medications (other than anti-depressants or ADHD medications). Use of opiates for pain, anti-depressants, ADHD medications, menstrual cycles, and birth control medications will be tracked during the study. Specific criteria for study participants are listed below.

### **Criteria for inclusion in the study are:**

1. Must be between the ages of 21 and 70 and provide informed consent;
2. Must report at least moderate anxiety ( $\geq 5$  on GAD-7);
3. Users (cannabis group) must have used marijuana at least once;
4. Users (cannabis group) must have a desire to use marijuana to cope with anxiety;
5. Non-users (non-cannabis, control group) must not have used marijuana for prior 6 months;
6. Non-users (non-cannabis, control group) must not have a desire to use marijuana to cope with anxiety;
7. Must report not using other drugs (cocaine, methamphetamine) in the past 72 hours and must not test positive on a urine toxicology test for drugs of abuse at the Baseline Appointment;
8. Must not be using psychotropic, steroid-based medications, or maximal doses of non-steroidal anti-inflammatories (NSAIDs), however anti-depressants and ADHD medications are ok;
9. Must not have immune-relevant disease (e.g. HIV) or be using anti-viral medications;
10. Must not be a regular tobacco user ( $\leq 4$  days per week; cigarette, E-cigs, or smokeless);
11. Must have a breath alcohol level of 0 at screening (to sign consent form);
12. Must not be actively seeking or in treatment for any substance use disorder (drug use levels will be carefully monitored via Timeline Follow Back (TLFB) throughout the study to assess any confounding influences of drug or alcohol use);
13. Female subjects must not be or trying to become pregnant (as indicated by a Pregnancy test & Screening form administered at Baseline)
14. Must not be in treatment for psychotic disorder, bipolar disorder, or major depression disorder with suicidal ideation; or a history with these disorders.

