Marijuana is approved for medical use in over half the states and is gaining traction for use as an "off-label" add-on therapy for treatment-resistant anxiety and stress-related disorders. Paradoxically, however, while data suggest that marijuana, in particular Δ9-tetrahydrocannabinol (THC), increases anxiety acutely, cross sectional and longitudinal data suggest associations between marijuana use and *lower* risk for anxiety disorders. Such findings imply biological and/or behavioral changes in the post-intoxicated state that impact anxiety related processes. In light of considerable evidence that inflammation plays a pivotal role in the etiology of anxiety disorders and the putative anti-inflammatory properties of marijuana, we propose that the anti-inflammatory properties of marijuana are linked with its anxiolytic effects. Importantly, prior work has not considered that the anxiolytic effects of marijuana are the compound action of different cannabinoids, which vary in their pharmacology and effects. Specifically, cannabidiol (CBD), a non-psychotomimetic component of marijuana (doesn't produce a "high"), is thought to have anxiolytic properties and may mitigate some of the harmful effects of THC. Further, preliminary data, including our own, suggest that THC and CBD render differential effects on anxiety-related processes, such as effects on inflammatory and stress responses. Differences in inflammation likely impact processes such as the degree of stress-reactivity and acute and/or chronic variability in anxiety. Therefore, the degree to which different types of marijuana influence stress-response and inflammation may have a large and clinically-relevant impact on the effects of marijuana on anxiety. We propose to systematically examine the effects of cannabinoids on anxiety, inflammation, and stress reactivity in mild to moderately anxious (Generalized Anxiety Disorder (GAD-7)  $\geq 5$ ) marijuana users.

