**Hypothesis 1.** Based on numerous studies, including our own pilot data, that suggest CBD may be anxiolytic and mitigate the harmful effects of THC, we hypothesize a step wise effect of strain such that the -THC/+CBD group will demonstrate the lowest anxiety, as compared to the +THC/+CBD group(s), which will have lower anxiety levels than the +THC/-CBD and non-using control groups. *In addition to strain assignment, CBD and THC blood levels will also be tested in relation to anxiety, with greater CBD levels associated with lower levels of anxiety.*

**Aim 2:** Based on the notion that CBD decreases inflammation and acute stress, the study will examine: **1) circulating inflammatory markers and 2) behavioral and biological markers of stress reactivity** in mild to moderately anxious marijuana users exposed to one of three marijuana strains: 1) +THC/-CBD, 2) +THC/+CBD, or 3) -THC/+CBD versus a matched (non-using) group.

**Hypothesis 2A.** There will be a main effect of strain such that the -THC/+CBD group will have the lowest levels of circulating peripheral inflammatory markers, as compared to the +THC/+CBD group(s), which will have lower levels than the +THC/-CBD and non-using control groups. *In addition to strain assignment, CBD and THC blood levels will also be tested in relation to inflammation, with CBD levels associated with lower levels of inflammation.*

**Hypothesis 2B.** There will be a main effect of strain such that the -THC/+CBD strain group will have the lowest levels of stress-reactivity to a laboratory stressor (measured via self-report, physiological, and inflammatory stress responses), as compared to the +THC/+CBD group(s), which will have lower levels of reactivity than the +THC/-CBD and non-using control groups. *In addition to strain assignment, CBD and THC blood levels will also be tested in relation to stress-reactivity outcomes, with CBD levels associated with less stress-reactivity.*

**Aim 3:** Based on the notion that the effects of CBD on inflammation or stress may mediate the effects of marijuana on anxiety, the study will **examine the mechanisms by which CBD influences anxiety.**

Hypothesis 3. We will estimate a mediational model that tests whether the effect of marijuana strain on anxiety is mediated by changes in circulating inflammatory markers, stress-reactivity, or both.

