#### **IV. RESEARCH STUDY DESIGN**

---

**Overview and Design of the Proposed Study.** Consistent with our preliminary study, we will recruit (from the Denver and Boulder areas): 450 participants who report a desire to use marijuana to cope with their anxiety, have had previous experience with marijuana, and report a Generalized Anxiety Disorder-7 (GAD-7) score of  $\geq 5$  (at least mild to moderate anxiety) and 75 non-using cannabis controls (matched for anxiety via GAD-7  $\geq 5$ ) who do not report an intention to use marijuana to cope with their anxiety nor any marijuana use over the prior six months. A summary of the Assessment schedule and the additional inclusion/exclusion criteria are detailed below in Table 1 and Section VI (respectively).

All participants will come to the CUChange Lab for a Baseline Appointment (Session 1) involving extensive measures of anxiety (e.g., Depression, anxiety, and stress scale, a rumination induction task, a dot probe task, rumination self-report scale, etc.) and other psychiatric symptoms, health behavior (e.g., stress, quality of life, sleep, alcohol use), the cognitive testing battery utilized in our preliminary studies, a blood draw for biomarkers of inflammation, and a motor battery (**Baseline Appointment, Session 1**). During this Baseline Appointment, a research assistant will provide information on three at-home aspects of the study: 1) the range of assigned cannabis products (e.g., differing THC to CBD ratios possible) and potential prices, 2) the ActiGraph wearable watch device that participants will be loaned to measure physical activity and sleep (during the final 2 weeks of the four week study), and 3) a microbiome collection kit that they will be given to complete (once before and once after 4 weeks of *ad libitum* use of their cannabis product). The experimental aspect of this study will be the assigned cannabis ratio, while the other aspects of this study are *ad libitum* based, with regard to the dosing schedule and choice of product type (flower or edible), by participants that would already like to use cannabis to cope with their anxiety.

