All of these advertisements will describe the opportunity to contribute to research regarding cannabis use. Specifically, the posts on social media will include the following wording “The University of Colorado is conducting research on how levels of CBD and THC are related to anxiety and stress.” All social media pages will provide additional information about the study (see attached word flyer). The wording used on the social media page may also be used in flyers or other advertisements.

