After completing the final blood draw, subjects will receive training in the use of online daily assessments (see details below) and the three user groups will then be assigned a marijuana strain to use for the next four weeks instead of their typical strain. Marijuana using participants will be

randomly assigned to one of three marijuana strains (a THC-based strain akin to a typically used strain with normal levels of THC and little to no CBD, a THC and CBD strain in combination, with a 1:1 ratio between THC and CBD levels, or a CBD-enriched strain with little to no THC, and then given instructions to purchase their assigned strain (labeled either C, D, or E) at a good clinical practice local dispensary. Marijuana users will be asked to use their assigned strain (and only that strain) as they wish over the course of the next four weeks. Non-users will be asked to continue to abstain from marijuana use over the next four weeks. After completing the measures and procedures, research study staff will answer any questions subjects have on their daily messages (see details below), debrief participants, and compensate them with \$80 in cash for their time and effort during the Baseline Appointment. Lastly, each participant will be scheduled for their 2-Week (Session 2) Apppintment at the CINC for two-weeks later.

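### Non-using controls are defined by marijuana only, so users of CBD sold in other forms could be counted as unexposed in the user v control comparisons of stress reactivity

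*Combined protocol and SAP*

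**What the plan says.** Every rule that makes someone a control is written in terms of marijuana.

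- Section VI, inclusion criterion 5: "Non-users (non-cannabis, control group) must not have used marijuana for prior 6 months".
- Section VI, inclusion criterion 6: "Non-users (non-cannabis, control group) must not have a desire to use marijuana to cope with anxiety".
- Section IV, Overview and Design, describes the controls as reporting no intention to use marijuana for anxiety, "nor any marijuana use over the prior six months".
- Section XII, Baseline Appointment: "Non-users will be asked to continue to abstain from marijuana use over the next four weeks". Section IV also advises non-users to leave their behaviour as it is, and asks all groups to report any change.

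The agent expected to act is CBD. In Hypothesis 1 (section I), "we hypothesize a step wise effect of strain such that the -THC/+CBD group will demonstrate the lowest anxiety", and blood levels are to be tested "with greater CBD levels associated with lower levels of anxiety". Hypotheses 2A and 2B make the same prediction for inflammation and stress reactivity, and each names the non-using controls as a comparator.

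Blood cannabinoids are measured in all participants at baseline and at each later session (section XII). The analysis plan in section IV (Aims 1 and 2) tests blood CBD only within the marijuana users. No rule says what happens when a control has measurable CBD.

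**The concern.** A comparator for a CBD product should be free of CBD, and the plan does not quite secure that. The other screens do not clearly close the gap:

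- Criterion 8 bars psychotropic medication, but section I describes "cannabidiol (CBD), a non-psychotomimetic component of marijuana", so the bar does not plainly reach it.
- The urine panel in Table 2 gives marijuana among its examples and does not name CBD.
- The list of tracked medications in section VI does not include CBD.
- A control already taking CBD who follows the section IV advice not to change behaviour would simply continue.

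At stake is the meaning of the user v non-user comparison. If some controls already have part of the CBD effect, a small difference between the 0:1 or 1:1 group and the controls could reflect an exposed comparator, and the planned analyses would not show it.

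**Working it through.** **The plan's own figure.** Section IV states that 450 participants, four groups, three assessments and an ICC of .5 allow detection of a group-by-time effect of f = .09. The usual within-between formula has noncentrality f²·N·m/(1−ρ) = .0081 × 450 × 3 / .5 = 21.87 on 6 and 892 degrees of freedom. It gives power .958 at f = .09, and a smallest f of .071 at power .80. The stated figure is therefore not reproduced, though it errs on the safe side. A value of about .087 comes from N = 300, or from N = 450 with m−1 in place of m. This is a separate matter: f = .09 concerns the interaction, while the exposure problem bites on level contrasts. The readable text gives no detectable effect for Aim 2B.

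**Which analyses are exposed.** Let δ be the reduction due to CBD, p the share of controls taking CBD, and e the share of δ that they carry. Assume additive effects.

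- *Levels at one assessment.* The control mean is shifted by p·e·δ, so the contrast becomes δ(1 − p·e). This fits Aim 2B, which has one assessment point and no time term, and stress reactivity at Session 3 in Aim 3. The reactivity score is a difference across the induction within a session. It is not a difference from Session 1, so it does not remove a standing CBD effect on reactivity.
- *Change from Session 1, stable CBD use.* The shift e·δ is present at both sessions and cancels, so the contrast stays at δ.
- *Change from Session 1, CBD started on study.* The shift appears only later, and the contrast again becomes δ(1 − p·e).

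The group-by-time models and the Aim 3 changes in anxiety and inflammation fall under the last two cases. So does the .40 path, which runs from the 0:1 v control contrast to change in inflammation.

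**Illustrative size for a level contrast.** Inputs from section IV: two-tailed alpha .05; power .80; 0:1 group 75 + 50 = 125 (the 1:1 group is the same size); control 75. Inputs not in the documents: p from 0% to 30%, and e = 1 or .5.

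- Standard error in SD units: √(1/75 + 1/125) = .1461.
- Difference detectable with power .80: (1.960 + .842) × .1461 = .409 SD.
- Power after dilution: Φ(.409(1 − p·e)/.1461 − 1.960).
- Example, p = 10%, e = 1: .409 × .90 = .368; .368/.1461 = 2.52; 2.52 − 1.96 = .56; power .71.

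| Controls exposed | Power, full effect | Power, half effect |
|---|---|---|
| 0% | .80 | .80 |
| 5% | .76 | .78 |
| 10% | .71 | .76 |
| 20% | .61 | .71 |
| 30% | .50 | .66 |

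**What excluding exposed controls costs.** Ten per cent of 75 is 7.5, say 8, leaving 67. The standard error becomes √(1/67 + 1/125) = .1514. The undiluted difference gives .409/.1514 − 1.960 = .74, so power is .77, against .71 with exposed controls kept at full effect. This assumes that every exposed control is identified.

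**The case against.** The strongest reply is that the word marijuana is broad here. Section I lists the 0:1 product among the marijuana ratios, section XII counts the CBD-enriched strain as one of three marijuana strains, and criteria 5 and 6 label the controls as non-cannabis. This stands for CBD strains sold as marijuana. A reader might infer that anyone on a CBD-only product can enter as a control; the documents do not support that. The remaining gap is CBD sold as something else, which they never mention.

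There are also partial safeguards. Advice not to change behaviour discourages starting CBD on study, and changes are to be reported. Table 1 sends daily reports to all participants, and the timeline follow-back covers other drugs. The screening form is not reproduced, so it may ask about CBD. None of these is a rule on CBD-exposed controls.

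A reader might also infer from the advertisement, which says the university is "conducting research on how levels of CBD and THC are related to anxiety and stress", that controls will be drawn from people already taking CBD. That is conjecture: the documents give no rate, and criterion 6 works against such selection to some degree.

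Finally, section IV treats the 1:0 arm as the naturalistic control and centres the primary hypotheses on switching users to 1:1 or 0:1. Those contrasts are randomised and do not involve the non-users. This stands in full.

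**Conclusion.** The gap is real but narrow. As written, the plan could treat controls who take CBD in other forms as unexposed, although it collects the blood data to detect at least some of them. If CBD acts as hypothesised, the 0:1 and 1:1 v control contrasts would be biased towards zero by the proportion p·e for Aim 2B and for stress reactivity at Session 3 in Aim 3. Hypotheses 1 and 2A are worded as levels, but the named primary test is group by time. There, and in the Session 1 to 3 change analyses, only CBD started or changed on study matters.

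Two stronger readings fail. Dilution does not run through all of Aims 1 to 3: stable use cancels from the change scores, including the .40 path. Nor could the trial as a whole miss a CBD effect for this reason, because the randomised strain contrasts and the blood-CBD models among users are untouched.

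The power figures are illustrative only. They rest on assumed exposure rates, an assumed share of the effect, and a level contrast that starts at the plan's .80.

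**What to change.** 1. Reword criteria 5 and 6 and the section XII instruction to controls so that they refer to *marijuana or any product containing CBD or THC*, and align the control description in section IV.
2. Add that item to the screening form and the timeline follow-back.
3. Keep all controls in the main analysis. Pre-specify a sensitivity analysis of the user v control contrasts that excludes controls with quantifiable CBD or THC at any of Sessions 1 to 3. State the assay limit that counts as quantifiable. The documents give no detection window, so a negative result should not be read as proof of no exposure.

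The cost is a phrase in two criteria and one instruction, one added item, and one analysis on an assay already run. The downside is a slightly smaller pool of eligible controls. The Spring 2023 update in section IV is contacting people who have already completed the study. If enrolment is over, the sensitivity analysis alone still applies.

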## **VII. VULNERABLE POPULATIONS**

---

This study does not include any vulnerable populations.

## **VIII. RECRUITMENT METHODS**

---

Recruitment will be via a number of sources that have been used successfully by our research team. First, as in our pilot project, we will recruit using flyers posted in and ads on the webpages and social media pages of dispensaries in the Denver and Boulder areas. Second, with assistance from local health care providers and physicians, we will advertise our study with flyers (see attached flyer) in and referrals from local mental health clinics. Third, we will utilize targeted mailings, advertising the opportunity to participate in our study. We will obtain a list of names and addresses of individuals who fit our target demographics and geographical area. These names/addresses are obtained from publicly available records purchased from a marketing firm (see <http://www.alescodata.com/reseller-programs.html>). Recruitment materials are mailed to each address on the list. We can narrow the list based on age, gender, geographic location, and other criteria. Fourth, we will use the NIH-funded free ResearchMatch (see <https://www.researchmatch.org/>) tool to link health criteria from potential participants to our specific research criteria. ResearchMatch has a large population of volunteers who have consented to be contacted by researchers about health studies for which they may be eligible. We will also advertise on free platforms like online patient groups and pay for platforms (e.g., Facebook/Twitter advertising) that often allow for targeting advertisements based on age, geographic location, and interests (e.g., following or “liking” posts related to anxiety).

In summary, we will recruit subjects locally and primarily through: target ads on anxiety groups in Facebook/Twitter, mailing flyers w/purchased names & addresses from Alesco and NIH-based ResearchMatch tool, flyers and referrals from providers’ offices (e.g., Clinical Psychologists), recreational and alternative health centers (e.g., yoga studios, acupuncture and massage specialists, and gyms, etc.), as well as in local restaurants and shops in Boulder. The combination of these varied recruitment methods should provide ample and steady potential participants, as in previous studies similar in size. All interested participants will be directed to complete an online screening survey (via RedCap) or to contact the CU Change Lab by phone or email (to be screened over the phone).

All of these advertisements will describe the opportunity to contribute to research regarding cannabis use. Specifically, the posts on social media will include the following wording “The University of Colorado is conducting research on how levels of CBD and THC are related to anxiety and stress.” All social media pages will provide additional information about the study (see attached word flyer). The wording used on the social media page may also be used in flyers or other advertisements.

## **IX. COMPENSATION**

---

Participants will receive \$335 at the end of the study. Given the amount of time required in the study and the travel to and from the lab for the first and second session, this is a reasonable amount of money to compensate participants for their time and effort. Thus, there is no question of coercion. Participants will receive \$80 in cash and for the Baseline Appointment (1st in-person Appointment at CINC), \$60 for the 2-Week Appointment (2nd in-person appointment at CINC), and \$80 for the 4-Week Appointment (mobile in-person appointment). Participants will also receive \$1/day for each of the *daily follow-up messages* that they complete during the *ad libitum* 4-Week period, with a possible bonus of \$10 for completing at least 26 of the 30 daily messages, for a maximum of \$40 extra paid in cash. This will be split between the 2-Week Appointment

(\$20 for daily messages 1-15, \$60 for Session 2, totaling \$80) and 4-Week Appointment (\$20 for daily messages 16-30, \$80 for Sessions 3 & 4, totaling \$100). Participants will receive a \$6 Grocery Store/Amazon.com gift card for the 1st part (questionnaires) of the 5 subsequent and brief *Monthly follow-up surveys* completed and a \$5 Grocery Store/Amazon.com gift card for the 2nd part (TLFB), with a bonus \$20 Grocery Store/Amazon.com gift card if the 1st (questionnaires) and 2nd part (TLFB) of all 5 *Monthly follow-up surveys* are completed (\$75 total, delivered online via email). If the 1st and 2nd part of only 4 out of 5 *Monthly follow-up surveys* are completed the participant will receive a \$15 bonus gift card instead. If a participant does not complete the study, payment will be pro-rated for the Appointments/online follow-up assessments that they do complete, in-person, and in cash. At request, participants may also receive complementary RTD/Bus transit passes to help with transportation to and from our facilities.

